#### 4.4 Sample Types and Numbers

Both AN swab specimens and comparator nasopharyngeal swab specimens will be collected for detection of SARS-CoV-2. Subjects will be enrolled in an "all comers" style, including both symptomatic and asymptomatic patients. The study population will include subjects from 2 years old to greater than 65 years old. Minors must be consented by their parent or legal guardian. The parent or legal guardian should collect the samples and perform testing if the child is between 2 and 13 years old. Older children ages 14-17 should collect their samples and perform their tests without their parent or legal guardian intervening. Enrollment efforts in various zip codes will be pursued in order to represent different socioeconomic and educational backgrounds and this information will be captured in the subject and tester questionnaires (Appendix 4 & 5). High risk individuals will not be excluded. Participants who regularly use home diagnostic tests, such as glucose meters, or are trained medical or laboratory professionals will be excluded.

Study testing will continue until at least 30 PCR confirmed positives are collected, 30 PCR confirmed negatives are collected, and 25 samples are collected from minors between the ages of 2 and 13. Ideally these 30 positives should include at least 10 asymptomatic PCR positive subjects. Specimen collection may be terminated once the 30 SARS-CoV-2 RNA positive specimens and 60 total specimens have been accrued preferably including at least 10 asymptomatic

positive subjects. The FDA may require additional enrollments in order to collect at least 10 asymptomatic positive subjects.

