#### 1.2 Intended Use

The MP Biomedicals Rapid SARS-CoV-2 Antigen Test is an immunochromatography based one step in vitro test intended to detect nucleocapsid antigen from the SARS-CoV-2 virus that causes COVID-19. It is designed for over the counter (OTC) rapid qualitative determination of SARS-CoV-2 virus antigen in anterior nasal swabs from individuals within 7 days of symptom onset or without symptoms or other epidemiological reasons to suspect COVID-19 infection. This test is for non-prescription home use with self-collected anterior nasal swab specimens directly from individuals aged 14 years and older or with adult-collected anterior nasal samples directly from individuals aged 2 years or older.

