#### 2.2 Study Objectives

The objective of the study is to evaluate the feasibility of using Rapid SARS-CoV-2 Antigen Test detection of SARS-CoV-2 virus in OTC home use. The presence of SARS-CoV-2 virus will be confirmed by PCR methodology. Testing will be performed with EUA PCR tests. The acceptance criteria for this study is Positive Percent Agreement (PPA) greater than or equal to eighty percent and Negative Percent Agreement (NPA) greater than or equal to ninety-eight percent).

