#### 4.3 Specimen Collection

Each study volunteer who agrees to participate in the study will be asked to complete an Informed Consent Form (Appendix 7). A parent or guardian will need to consent for subjects under 18 years old. Study subjects between the ages of 7 and 13 years old will be asked to complete an age-appropriate Assent form (Appendix 8). Study subjects between ages 14 and 17 will complete the assent portion of the Informed Consent Form (Appendix 7). Minors between the ages of 2 and 13 years old will have their samples collected and tested by a parent or legal guardian. Minors between the ages of 14 and 17 will collect and test their own samples without interference from their parents or legal guardians. Specimens will be collected and tested only after the Informed Consent form is completed.

Each testing participant will be asked to complete a tester information form assessing basic demographics and socio-economic questions (Appendix 3). Each subject being tested will be asked to complete a subject information form describing any symptoms of respiratory illness and/or resent exposure to confirmed COVID-19 positive individuals within the last two weeks (Appendix 4). If the tester is self-collecting, then they skip the second half of the subject information form as indicated on the form due to redundancy of demographic and socio-economic information recorded on the tester information form. Subjects and testers will be observed by EDP Biotech Corp. personnel or designees during sample collection and testing process in person. The same unique study ID number will be associated with all forms and documents related to a single valid Rapid SARS-CoV-2 Antigen test result.

The NP swab collection will not provide participants additional training because the collection technique differs from AN collection. Participants will be reminded that the study representative is performing a different collection technique for a different test and that the participant should refer only to the instructions for use for the proper collection technique.

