- The sensitivity, specificity, and 95% confidence intervals for each category of days post-symptom onset will be calculated based on the cumulative number of subjects who fit into that category.
- The subjects considered symptomatic will also be separated into the following categories in order to calculate the sensitivity and its 95% confidence interval based on non-cumulative reported days post-symptom onset:
 - 0
 - 1
 - 2
 - 3
 - 4
 - **5**
 - 6
 - 7
 - 8 to 14
- Analysis for sensitivity, specificity, and 95% confidence intervals based on presence of symptoms or reported exposure and based on absence of symptoms or reported exposure.
 - Subjects considered symptomatic according to the November 9, 2021 FDA EUA guidance will be collectively analyzed for sensitivity and specificity using the above formulas.
 - Subjects considered asymptomatic according to the November 9, 2021 FDA EUA guidance will be collectively analyzed for sensitivity and specificity using the above formulas.
- Analysis will also be conducted for all subjects (total sample size of 188), regardless of categorization, using the same above formulas for sensitivity, specificity, and the 95% confidence intervals.
- Overall positivity rate for the subject population will be calculated based on age group and reported gender.
 - Age groups will be separated based on the November 9, 2021 FDA EUA guidance into the following categories:
 - 2 to 13 years of age
 - 14 to 24 years of age
 - 25 to 64 years of age
 - 65+ years of age
 - Gender will be separated into male and female. No consideration will be given to gender identity or categories other than male and female.
 - Positivity rate will be calculated based on the results of the comparator method(s) used to gauge the efficacy of the candidate device.
 - This will be calculated for each of the above age groups, as well as for the subject population overall. The total number of subjects in each age group who test positive on the candidate device will also be calculated.
 - The total number of males and females in the study population will be calculated, and further separated by the above age groups.
- Analysis for sensitivity and 95% confidence intervals based on comparator cycle threshold (Ct) value will be conducted as follows:

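### Protocol section 4.4 gives two conflicting stopping rules, and the weaker one allows collection to end without the 25 samples from ages 2 to 13 that the other requires

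*Protocol*

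**What the plan says.** Both rules stand in one paragraph of Protocol section 4.4.

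- **First rule, mandatory.** "Study testing will continue until at least 30 PCR confirmed positives are collected", and the same sentence goes on: "30 PCR confirmed negatives are collected, and 25 samples are collected from minors between the ages of 2 and 13". All three counts must be reached.
- **A preference between the two rules.** "Ideally these 30 positives should include at least 10 asymptomatic PCR positive subjects".
- **Second rule, permissive.** "Specimen collection may be terminated once the 30 SARS-CoV-2 RNA positive specimens and 60 total specimens have been accrued". The asymptomatic preference is repeated here. The child minimum and the minimum of negatives are not.

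Four other places bear on the point.

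- Protocol section 4.3 says who handles the children's samples: "Minors between the ages of 2 and 13 years old will have their samples collected and tested by a parent or legal guardian". Ages 14 to 17 collect and test their own.
- Protocol section 1.2 claims use "with adult-collected anterior nasal samples directly from individuals aged 2 years or older".
- Protocol section 2.2 sets the pass mark on overall agreement: "The acceptance criteria for this study is Positive Percent Agreement (PPA) greater than or equal to eighty percent", with an NPA of at least 98%.
- The SAP repeats neither stopping rule. It gives an all-subjects total of 188 and uses age groups only for positivity rates and counts: "Overall positivity rate for the subject population will be calculated based on age group and reported gender".

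**The concern.** The two rules disagree about when collection may end. A team holding 30 positives, 30 negatives and 24 samples from ages 2 to 13 is told by the first to go on and by the second that it may stop. Nothing in either document ranks them.

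What is at stake is evidence for one part of the intended use. Ages 2 to 13 are the only subjects whose swabs are taken and tested by a parent or guardian, and the 25 samples are the only number the plan sets for them. Enrolment is otherwise open to all comers, so no other provision guarantees that count. Protocol section 4.0 says the data may go into a regulatory filing. A shortfall in children that the protocol itself allowed would then be hard to defend.

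**Working it through.** **1. The plan's own total.** The first rule's minimums give 30 + 30 = 60, the total named in the second rule. The figure of 60 is therefore consistent with the positive and negative minimums. The child minimum adds nothing to it, because the 25 children can be among the 60.

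**2. The rules side by side.** Let P be the positives, M the negatives and K the samples from ages 2 to 13.

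- Rule 1: P ≥ 30, M ≥ 30 and K ≥ 25.
- Rule 2: P ≥ 30 and P + M ≥ 60.

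| P, M, K | Rule 1 met | Rule 2 met |
|---|---|---|
| 30, 30, 25 | yes | yes |
| 30, 30, 24 | no | yes |
| 30, 30, 0 | no | yes |
| 40, 20, 25 | no | yes |

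Meeting rule 1 always meets rule 2, since P ≥ 30 and M ≥ 30 imply P + M ≥ 60. The reverse fails. Rule 2 is strictly weaker.

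**3. Chance of a child shortfall at the earliest stop under rule 2.** The documents give neither the PCR positivity p nor the child share c, so both are assumed. The model also assumes that child status is independent of PCR result and that no recruitment is aimed at children. Let T be the number of subjects needed to reach 30 positives (negative binomial with parameters 30 and p). Collection can first stop at N = max(60, T). Then

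P(K < 25) = Σ over T of P(T) × P(Binomial(N, c) ≤ 24).

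| Child share c | p = 16% | p = 20% | p = 30% |
|---|---|---|---|
| 15% | 31% | 66% | 98% |
| 20% | 5% | 22% | 82% |
| 30% | 0.03% | 0.6% | 20% |

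The expected N is 187.5, 150 and 100 at the three positivity values. The 16% column thus corresponds to a study of about the SAP's size.

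**4. If enrolment ran to the SAP's 188 whatever the stopping rule.** Reaching 25 children on average needs a share of 25/188 = 13.3%. P(Binomial(188, c) ≤ 24) is about 23% at c = 15%, 0.6% at 20% and under 0.0001% at 30%.

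**5. How likely a stop at exactly 60 is.** It needs at least 30 positives among the first 60. The chance is 0.09% at p = 30%, about 2 in 10 million at 20% and about 1 in a billion at 16%.

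**6. Shortfall in negatives.** Fewer than 30 negatives at the earliest stop needs 31 or more positives among the first 60. The chance is 0.04% at p = 30% and 4.4% at p = 40%.

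**The case against.** The best answer is that the sentences can be read together. The first is mandatory and the second permissive, and a team that follows the first satisfies both. The second refers back to the 30 positives, and its 60 is 30 + 30, so it may be shorthand for the positive and negative quotas. That may well be what was meant, but the text does not say so. On that reading the second sentence also has no effect, because meeting the first already gives 30 positives and 60 in total. It has effect only where it lets collection stop sooner. It repeats the asymptomatic preference yet omits the child minimum, so a reader could take the omission as deliberate.

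A second answer is the SAP's total of 188, over three times 60. It makes a shortfall less likely at a given child share (step 4). But the SAP presents it as the number to be analysed and not as a stopping rule, does not say how it was reached, and sets no number for ages 2 to 13. It does not settle which rule governs.

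A third answer is that a team with a stated target of 25 children would recruit for it. This is fair, and it would lower every probability in step 3. Those figures show how the risk varies with the assumptions. They do not forecast it.

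**Conclusion.** The conflict is real as written: a stated stopping rule permits breach of a stated minimum. That conclusion rests on the wording alone and needs no assumption. Its practical size is uncertain. Over the assumed ranges the chance of a child shortfall runs from negligible to near certain, and the documents do not narrow it.

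Three stronger readings are not supported.

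- A reader might infer that the study is likely to stop at 60 subjects, where 25 children would be 25/60 = 42% of enrolment. At the positivity values used here a stop at 60 is almost impossible (step 5), and the SAP's total is 188.
- A reader might infer that the pass/fail result is in doubt. It is not: the acceptance criteria are overall PPA and NPA, and the SAP plans no agreement analysis by age group. What is at risk is support for adult-collected samples in the youngest group.
- A reader might give the possible shortfall in negatives equal weight. It is minor unless positivity is around 40% or higher.

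The point should be fixed because the repair is one sentence and enforces a commitment the protocol already makes.

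**What to change.** Delete the sentence in Protocol section 4.4 that permits termination, or make it conditional on every minimum. For example: *Collection may end only when at least 30 PCR positives, at least 30 PCR negatives and at least 25 samples from ages 2 to 13 have all been obtained, preferably with at least 10 asymptomatic positives.* Also reconcile section 4.4 with the SAP by stating what the total of 188 represents and how it relates to the stopping rule.

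The cost is the option to stop before 25 children are enrolled, and possibly longer enrolment. Under the model in step 3, the expected extra enrolment is E[max(0, 25 − K)]/c, with K counted at the earliest stop under the second rule:

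| Child share c | p = 16% | p = 20% | p = 30% |
|---|---|---|---|
| 15% | 9 | 25 | 67 |
| 20% | 0.7 | 4 | 27 |
| 30% | under 0.1 | under 0.1 | 2.4 |

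Recruitment aimed at children would reduce these numbers. The smallest possible total stays at 60.

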#### 4.5 Exclusion criteria

Subjects less than 2 years old will be excluded. Participants with prior medical or laboratory training or prior experience with self-collection or self-testing (including infectious disease home tests) will be excluded. High risk individuals will not be excluded unless they are too young or have prior training or experience that would exclude them.

#### 4.6 Sample Handling and Management

Nasopharyngeal swab specimens after collection will be labeled and stored at 2-8°C prior to shipment on ice packs and testing.

Study specimens will be accessioned into either the DMH Premier Laboratories system (comparator nasopharyngeal swab samples) or the EDP Biotech Corp. system using assigned unique identifying number to facilitate tracking and identification during analysis. A visual inspection of the specimens will be made to ensure the specimens meet study requirements for volume content and proper appearance. Specimens may be stored refrigerated (2-8°C) prior to testing per the testing protocols for each specimen type.

Remnant samples will be maintained frozen for the duration of the study in case they are needed for repeat and/or discordant testing. Following completion of the study remnant NP samples will be labeled with the subject's unique study ID number which does not visually link to the study subject and stored in -80C freezers for as long as space permits for future research testing.

# 5.0 Sample Preparation and Testing Procedure

#### 5.1 Rapid SARS-CoV-2 Antigen Test

The study participant will collect the AN swab sample and perform testing according the provided instructions for use without assistance from study personnel other than to refer the participant to the IFU for guidance.

# 5.2 Instrument Set-Up (Calibration and Quality Control)

All instrument quality control and calibration procedures will be performed per manufacturer's recommendations or the laboratory's QA/QC manual, as appropriate. Instrument calibration and instrument performance will be documented on each day that testing is performed. All documentation related to

the operation of the instrument will be completed, verified and recorded per the laboratory's standard procedures.

#### 5.3 Reagent Preparation

Ag reagents will be prepared for use by EDP Biotech Corp. laboratory personnel as specified in their respective manufacturer's package insert/instruction for use documents. PCR reagents will be prepared for use by DMH Premier laboratory personnel as specified in their respective manufacturer's package insert/instruction for use documents.

#### 5.4 Specimen Processing

Premier Laboratories or Premier Laboratories personnel will process the collected nasopharyngeal swab specimens upon receipt. EDP Biotech Corp personnel will process the collected AN swab specimen data as it is generated.

#### 5.5 Sample Preparation

SARS-CoV-2 RNA will be extracted from the collected specimens using procedures provided by the EUA PCR kit manufacturers. The specifications for specimen integrity described in the manufacturer's instrument instructions will be followed, i.e., storage conditions prior to testing.

#### 5.6 Sample Transport

Specimens must be packaged, shipped, and transported according to the current edition of the International Air Transport Association (IATA) Dangerous Goods Regulation. Follow shipping regulations for UN 3373 Biological Substance, Category B when sending potential 2019-nCoV specimens. Store specimens at 2-8°C and ship overnight to Premier Laboratories on ice pack. If a specimen is frozen at -70°C or lower, ship overnight to Premier Laboratories on dry ice.

#### 5.7 Sample Storage

Remnant NP samples will be stored at -80°C in for the duration of the study in case they are needed for re-testing of discrepant results. Following completion of the study, samples will be maintained at -80°C while space permits in case they are needed for future testing. Remnant NP samples will be labeled with the unique study ID number and/or a random ID that does not visually link to the study subject.

#### 5.8 Control/Calibrator Preparation

Assay controls will be included in each test run per manufacturers' directions.

#### 5.9 Assay Testing

Testing of the study specimens will be performed as follows:

Nasopharyngeal swab specimen after transport will be evaluated at Premier Laboratories with the

CDC 2019-nCoV Real-Time RT-PCR Diagnostic Panel (CDC). Testing will be performed according to the specific Premier Laboratories Standard Operating Procedures associated with this test (see Appendices 1 and 2).

AN swab specimens will be evaluated at the time of collection by study subjects observed by EDP Biotech Corp. personnel or designee. Specimens will be tested per the manufacturer's product instructions (Appendix 7).

#### 5.10 Discrepant Analysis

Discordant results will be re-tested using the CDC's Influenza SARS-CoV-2 (Flu SC2) Multiplex Assay FDA EUA SARS-CoV-2 RT-PCR assay performed by Premier Laboratories. Results from a Discrepant analysis should not be included in the calculation of negative percent agreement (NPA) and positive percent agreement (PPA) but may be added to the performance table as a footnote.

#### 5.11 Reporting of Results

The results obtained with the Rapid SARS-CoV-2 Antigen Test will be captured electronically in the EDP Biotech Corp. LIMS system by observers. Premier Laboratories and/or Premier Laboratories will provide the data from the nasopharyngeal swab specimen testing in an electronic format. The result of the comparator PCR test will be reported to the subject and/or their health care provider.

#### 5.12 Adverse Events (AEs)

This is a non-significant risk device study. The study presents no potential for serious risk to the health, safety, or welfare of any human subject as it uses only commonly employed techniques for the NP and AN swab specimens. Since the study procedures are not greater than minimal risk, Serious adverse events (SAEs) are not expected. If any unanticipated problems related to the research involving risks to subjects or others happen (including SAEs) these will be reported to the IRB, Office for Human Research Protections (OHRP), and the study sponsor. AEs that are not serious but that are notable and could involve risks to subjects will be summarized in narrative or other format and submitted to the IRB, OHRP, and sponsor at the time of continuing review.

#### **5.13** Device Malfunctions

Any invalid results of the Rapid SARS-CoV-2 Antigen Test will be repeated, and the repetition noted. Any invalid results of the nasopharyngeal swab comparator will also be repeated, if possible.

# 6.0 Data Management and Analysis

#### 6.1 Sample ID Numbers and Identification

Each study site will receive a list of randomly generated non-repeating unique study ID numbers (MPB-014-###, if the study size and or duration is increased, then additional digits may be added). The same study ID number will be assigned to all documents and forms associated with a single valid Rapid SARS-CoV-2 Antigen test result including informed consent and authorization forms, assent forms, tester information form, subject information form, user comprehension assessment, and any other documents associated with each valid Rapid SARS-CoV-2 Antigen test result.

Each sample entered into the study will be tracked by the study ID number during accessioning. A data management log listing each sample number and storage information will be maintained.

#### 6.2 Data Evaluation and Accessibility

A report tabulating and analyzing the data will be prepared by the Clinical Investigator including tables of the results and a description of any deviations from the protocol.

#### 6.2.1 Acceptability of Data for Analysis

Valid individual specimen results generated in invalid runs are not acceptable for inclusion in final data analysis. Samples tested in invalid runs must be re-tested if the remaining specimen volume is available. Only valid results from specimens in valid runs will be included in the final data analysis.

#### 6.2.2 Exclusion of Data from Analysis

Data from invalid runs results will be excluded. All excluded results will be documented with rationale for exclusion and a summary of these cases will be provided.

#### **6.2.3** Data Entry and Corrections to Study Documents

All entries must be legible and made in indelible ink (preferably black); do not use pencil. Strike incorrect entries with a single line (do not obliterate or put "white-out" on the original entry). Then enter the correct information next to the original entry, initial, and date the correction.

